15.1.8 Events over Time - Expansion Part

Swimlane plots in which each lane documents the individual subject experience on a trial over time will be created for all confirmed responder subjects. The plots will include ontreatment, off-treatment periods, response according to RECIST 1.1 (investigator assessment), clinical progression and NLCB.

The no longer clinically benefitting (NLCB) reporting metric is defined as the date and the specific reason(s) a therapy was ultimately discontinued (end of treatment visit date).

15.2 Overall Survival

Overall survival is defined as the number of days from date of first IMP administration to death.

Overall survival will be presented using the same statistical methodology as for PFS except that censoring will not be applied neither when visits are skipped nor when new anti-cancer therapies are given. Subjects alive at the time of the analysis will be censored at minimum(cut-off date, last contact date).

The outputs will be repeated for the subgroups defined for cohorts 2 and 8 and for cohort 6 as mentioned in section 4.4.

15.3 Immunogenicity of Enapotamab Vedotin

Data on immunogenicity (anti-drug antibodies) of enapotamab vedotin will be listed only.

All details including presence of neutralizing antibodies (negative/positive) and titers of enapotamab vedotin will be listed.

TPL N°: eTPL SA-02-01 TPL Version: 02 Of SOP SA-02.08

TPL Effective Date: 31 Mar 2016

Approved in Vault: 6/30/2021

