### 4.2 Secondary Objectives

- To evaluate the safety laboratory parameters of enapotamab vedotin in a mixed population of patients with specified solid tumors.
- To establish the PK profile and evaluate immunogenicity of enapotamab vedotin after single and multiple infusions.
- To evaluate the antitumor activity of enapotamab vedotin in a mixed population of patients with specified solid tumors.
- To evaluate Axl expression in tumor biopsies from a mixed population of patients with specified solid tumors.

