### 4.5 Secondary Endpoints

- Safety laboratory parameters (hematology and biochemistry).
- PK parameters (clearance, volume of distribution and area-under-the-concentration-time curve [ $AUC_{0-Clast}$  and  $AUC_{0-\infty}$ ], maximum concentration [ $C_{max}$ ], time of  $C_{max}$  [ $T_{max}$ ], pre-dose values, and half-life of enapotamab vedotin and free toxin [MMAE]).
- Immunogenicity of enapotamab vedotin (anti-drug antibodies).

Document Name: GCT1021-01 Protocol

Document Number: TMF-03326

Version: 11.0

---

- Anti-tumor activity measured by tumor shrinkage (based on computerized tomography [CT]-scan evaluations), as well as change in CA 125 in patients with ovarian cancer and change in prostate specific antigen (PSA) in patients with castration-resistant prostate cancer (CRPC).
- Objective Response, Progression-Free Survival (PFS), Duration of Response (DoR) and Overall survival (OS).
- Axl expression in the tumor biopsy.

[figure not shown]

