### **10.3.10 Immunogenicity of Enapotamab Vedotin**

Titers of enapotamab vedotin will be listed and positive/negative host immune response to enapotamab vedotin and presence of neutralizing antibodies will be summarized (positive/negative). Presence of PK-concentrations above a certain threshold, that depends on the drug tolerance of the ADA assay, at the same time as the ADA sample may make the ADA undetectable and hence render non-conclusive. The association between positive/non-positive ADA and PK (pre-dose, AUC,  $C_{max}$ ), major safety signals (CTCAE  $\geq$  Grade 3) and efficacy information (change in tumor size by CT scan) will be explored.

Document Name: GCT1021-01 Protocol

Document Number: TMF-03326

Version: 11.0

---

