### **10.6 Subgroups and Site Effects**

Subgroup analyses for the following factors are planned:

- Cancer type
- ADA-positivity (only for  $\geq$  Grade 3 AEs and tumor shrinkage endpoints)

Document Name: GCT1021-01 Protocol

Document Number: TMF-03326

Version: 11.0

---

Other sub-group analyses may be performed post hoc. Due to the low expected number of patients per site no investigation of side effects are planned.

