3.1.2 Secondary Objectives

- To evaluate the safety laboratory parameters of enapotamab vedotin in a mixed population of subjects with specified solid tumors.
- To establish the pharmacokinetic (PK) profile and evaluate immunogenicity of enapotamab vedotin after single and multiple infusions.
- To evaluate the antitumor activity of enapotamab vedotin in a mixed population of subjects with specified solid tumors.
- To evaluate Axl expression in tumor biopsies from a mixed population of subjects with specified solid tumors.

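### The SAP reduces immunogenicity, a retained secondary objective, to a listing; the protocol plans a summary, an exploration and a subgroup, and SAP 4.9 does not record the change

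*SAP*

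**What the plan says.** **Objective and endpoint.** Protocol 4.2 sets the secondary objective: "To establish the PK profile and evaluate immunogenicity of enapotamab vedotin after single and multiple infusions". Protocol 4.5 names the matching endpoint: "Immunogenicity of enapotamab vedotin (anti-drug antibodies". SAP 3.1.2 keeps the objective, again undertaking to "evaluate immunogenicity of enapotamab vedotin after single and multiple infusions".

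**Protocol analysis.** Protocol 10.3.10 lists titers and then commits to more: "positive/negative host immune response to enapotamab vedotin and presence of neutralizing antibodies will be summarized (positive/negative". It goes on: "The association between positive/non-positive ADA and PK" (pre-dose values, AUC and Cmax), together with CTCAE Grade 3 or higher signals and "efficacy information (change in tumor size by CT scan) will be explored". It also cautions that enough circulating drug at the time of an ADA sample may leave antibodies undetected and the result inconclusive. Protocol 10.6 plans two subgroup factors. One is cancer type; the other begins "ADA-positivity (only for" and is limited to Grade 3 or higher AEs and tumor shrinkage.

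**SAP analysis.** SAP 15.3 says: "Data on immunogenicity (anti-drug antibodies) of enapotamab vedotin will be listed only". Neutralizing-antibody status and titers get the same treatment.

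**The concern.** A SAP normally puts the protocol's planned analyses into operation. Here it keeps the immunogenicity objective but replaces the planned analysis with a listing. A listing gives results subject by subject. It gives no count or percentage of ADA-positive subjects, by dose or overall, and does not relate antibody status to exposure, toxicity or tumor response.

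The second issue is traceability. SAP 4.9 exists to tell the reader where the analysis departs from the protocol. If a secondary endpoint loses its summary without an entry there, someone reading the clinical study report against the protocol cannot tell a decision from an oversight.

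**Working it through.** No formula applies. The check sets each protocol commitment beside the corresponding SAP text.

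| Protocol commitment beyond a listing | Visible in the SAP? | Recorded as dropped in SAP 4.9? |
|---|---|---|
| Positive/negative summary of ADA response and neutralizing antibodies (10.3.10) | No; 15.3 excludes it | No |
| Exploration of ADA against PK, Grade 3 or higher signals and tumor size (10.3.10) | No | No |
| ADA-positivity subgroup for Grade 3 or higher AEs and tumor shrinkage (10.6) | No | No |

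Count: 0 of 3 visible, 0 of 3 recorded.

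1. **Output lists (SAP section 20).** The readable table and graph titles include no ADA item. The only immunogenicity output is Listing 16.02.02.05. The SAP addendum carries only the equivalent listing, A.16.02.02.05.

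2. **Subgroups (SAP 4.4).** Ten factors are named. Cancer type survives (for Cohort 6), but ADA-positivity does not appear. A general sentence permits other subgroups, including biomarkers. However, the outputs specified for subgroups are the forest plot of confirmed response, PFS and OS. None of these is Grade 3 or higher AEs or tumor shrinkage, so the general sentence does not restore the protocol 10.6 analysis.

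3. **Record of changes (SAP 4.9).** The section lists the added subgroups, the change to the Safety Set, and results cut back to listings: PSA, urinalysis, and the IRC best responses. Immunogenicity and the lost ADA subgroup are absent.

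4. **Protocol version.** SAP 4.9 compares itself with protocol version 10.0, whereas the protocol available is version 11.0. The Amendment 10 change table describes the statistical revisions as concerning the data cutoff, the reporting plan and the QTc report, under sections 10, 10.7 and 10.8. It names neither 10.3.10 nor 10.6, and both still stand in version 11.0. It is therefore reasonable to take them as unchanged from version 10.0.

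5. **Effect of Amendment 10 on ADA.** Protocol 16.3.8 ends further immunogenicity assessment. It withdraws no analysis of samples already taken.

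6. **Permission to drop.** Protocol section 10 lets the SAP add analyses. The allowance in 10.3.12 to defer analyses covers biomarker and pharmacodynamic work, not ADA.

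**The case against.** Four points can be made for the plan as it stands.

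**The data are still reported.** All ADA, neutralizing-antibody and titer results appear in the listing, and a reader could count the positives. This stands. One might infer that the trial would report nothing on immunogenicity, but the documents do not support that: the tabulated result is missing, not the data.

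**The exploration may sit elsewhere.** SAP 15.8 and section 18 are blacked out, several output titles are blank, and PK has its own non-compartmental and population plans. An ADA-PK analysis could be in any of these. This also stands, and it limits what can be said about the exploration. It helps the summary less, because SAP 15.3 says listing only, and it does not help SAP 4.9, which is readable.

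**Non-conclusive samples.** It is tempting to say that a listing hides samples affected by drug level and lets them pass as negative. The documents do not support this. Protocol 10.3.10 gives a caution, not a classification rule, and its own summary has only positive and negative categories. SAP 15.3 lists all details, and drug concentrations are in Listing 16.02.02.07. A per-sample listing conceals no more than the protocol's two-way table would.

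**Context.** The sponsor stopped development in November 2020, the trial is not randomized, and the ADA analyses are descriptive. This lowers the consequence and could justify a shorter analysis. It does not explain why the shortening goes unrecorded when the same step for PSA and urinalysis is declared.

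**Conclusion.** The point holds. SAP 15.3 conflicts with protocol 10.3.10, SAP 4.4 omits the subgroup planned in protocol 10.6, and SAP 4.9 records neither change. A retained secondary objective is left without a visible tabulated result.

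The loss of the summary and the silence of SAP 4.9 rest on readable text. That the exploration is absent is likely but not certain, given the redactions and the separate PK plans. The conclusion also assumes that protocol 10.3.10 and 10.6 read the same in version 10.0 as in version 11.0.

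The size is a count: three planned analyses, none visible and none recorded as dropped. The documents give no ADA rate, so the precision of an incidence estimate cannot be stated. The point deserves correction but is moderate in weight: it affects descriptive reporting and does not touch the DLT or adverse-event primary endpoints.

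**What to change.** 1. **Summary.** Add to SAP 15.3 and section 20 one table of ADA and neutralizing-antibody status, with positive and negative counts and percentages, by schedule and dose level and pooled. Flag results that may be inconclusive because of drug level, in line with the caution in protocol 10.3.10.
2. **Subgroup.** Restore ADA-positivity in SAP 4.4 for Grade 3 or higher AEs and tumor shrinkage, pooled across cohorts and subject to the existing minimum of 5 subjects. Name these two outputs explicitly, since the current subgroup outputs do not include them.
3. **Exploration.** Restore the comparison of ADA status with PK, Grade 3 or higher signals and change in tumor size, or cite the separate plan that covers it.
4. **Record.** Enter and justify in SAP 4.9 any of these that is dropped.

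The cost is small: one table, the pooled subgroup output and a short exploratory display, all from samples already collected. If the sponsor prefers to keep the listing alone, the minimum is the entry in SAP 4.9 with its reason. SAP addendum 2.1 says data up to the 22 March 2021 cut-off have already been reported, so the additions could be made through a further addendum, labelled as such.

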15.4 Anti-tumor Activity

Anti-tumor activity measured by tumor shrinkage (based on sum of the diameter(s) of all target lesions from the CT-scan evaluations) as assessed by the investigators for the Expansion part will be listed and summarized graphically:

- graphical plots:
 - waterfall plots of the best percent change from baseline. The bars will be marked by the best overall response according to RECIST 1.1 based on investigator assessment for the dose-escalation part and based on investigator assessment for the expansion part

Version: 4.0

Page 27 of 46

o individual profiles plots: spider plots summarizing the percent change from baseline of the sum of diameter(s) of all target lesions marking the lines based on the best overall response according to RECIST 1.1 based on investigator assessment for the dose-escalation part and for the expansion part.

15.5 CA-125 (Ovarian cancer only)

Descriptive statistics (actual values, change from baseline and percent change from baseline) will be presented for the dose escalation and expansion part.

Mean-se plots over time will be done for the actual CA-125 values and percent change from baseline. In addition, individual subject's data (percent change from baseline) by visit and dose level/cohort will be plotted in an individual profiles plot.

Waterfall plots of the maximum decline in CA-125 that occurs at any point after treatment start will be presented. The bars will be marked by the best overall response according to RECIST 1.1 based on investigator assessment for the dose-escalation part and for the expansion part.

In the listing of CA-125 the CA-125 responses, RECIST 1.1 responses and combined RECIST 1.1 - CA-125 responses will be added.

15.6 PSA (Prostate cancer only) – Expansion Part

The PSA data, when available, will be listed only. The listing will also include PSA responses (>50% reduction, 3-4 weeks apart) and RECIST 1.1 -based responses.

15.7 Tumor Axl-Expression – Expansion Part

Tumor Axl-expression measurements will be listed and summarized descriptively (by tumor type, by fresh/archived biopsy, by last treatment given before the biopsy was taken based on pre-defined groups).

The following parameters will be included:

- H-score quantified based on Axl positivity in
 - i) membrane,
 - ii) cytoplasm,
 - iii) membrane or cytoplasm (higher value of the two)

Descriptive statistics (actual values and percent change from baseline) will be presented to summarize the H-score parameters (for membrane and cytoplasm) at baseline and over time (archival and fresh screening results, cycle 2 and end-of-treatment results).

Mean-se plots over time will be done for the actual values and percent change from baseline.

TPL N°: eTPL SA-02-01 TPL Version: 02

Of SOP SA-02.08 TPL Effective Date: 31 Mar 2016

Box-and-whisker plot showing baseline expression of Axl (H-score) across cohorts will also be presented.

15.8	

16. Pharmacokinetics

The calculation of the pharmacokinetic endpoints will be performed by A separate PK analysis plan will be written by to describe the planned non-compartmental PK analyses for this trial.

PK concentrations and individual PK parameters will be analyzed on the PK Analysis set.

Individual plasma/serum concentration time curves of enapotamab vedotin (conjugated), enapotamab vedotin (total) and free toxin (MMAE), including information on actual dose, will be presented for all subjects in the PK set for the escalation part. All available data will be shown in these figures. The value <LLoQ will be replaced by the numerical LLoQ value divided by 2 and mentioned in a footnote.

The plasma/serum concentrations will also be summarized descriptively over time according to the schedule specified in section 8.1 of the protocol final version 10.0, dd. 9 December 2019. The number of subjects with an imputed LLoQ value will be added.

Mean-se graphs for the plasma/serum concentrations by cycle and dose level will be presented both with and without error bars.

In addition, descriptive statistics will be calculated and presented for all individual PK parameters (Cmax, $AUC_{(0-inf)}$, $AUC_{(0-last)}$, CL, $T_{1/2}$ and T_{max}) for cycle 1 and cycle 3 for the dose-escalation part. This will include mean (arithmetic and/or geometric), median, min, max, n, standard deviation (SD), and geometric coefficient of variation (CV%) of the PK parameters of enapotamab vedotin (conjugated) , enapotamab vedotin (total) (only for the final analysis) and free toxin (MMAE) provided by _______. Geometric mean and CV% will not be calculated for T_{max} and $T_{1/2}$.

Geometric CV% will be calculated as follows:

Geometric CV% = (sqrt(exp(variance for log transformed data)-1))*100

Mean-se graphs for the individual PK parameters (Cmax, $AUC_{(0-inf)}$, $AUC_{(0-last)}$, CL, $T_{1/2}$ and T_{max}) by cycle and dose level will be reported.

Page 28 of 46

TPL N°: eTPL SA-02-01 Of SOP SA-02.08 TPL Effective Date: 31 Mar 2016

Approved in Vault: 6/30/2021

17. Safety Evaluation

All results will be presented on the safety set (SAF).

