In order to obtain sufficient evaluable fresh tumor biopsies, up to 15 additional subjects may be recruited in Cohort 6 to ensure that 25 fresh biopsies are acquired. A maximum of 45 subjects may therefore be enrolled in Cohort 6. A higher number of biopsies are required in this cohort due to the mixture of tumor types being enrolled.

Cohort 8 will further explore the safety and efficacy of the 1.0 mg/kg 3Q4W schedule in NSCLC subjects without EGFR/ALK mutations. This is the same subject population as Cohort 2 where a preliminary efficacy signal was observed for the 1Q3W schedule. Cohort 8 will include up to 37 subjects with the aim to collect evaluable fresh tumor biopsies from 15 subjects. Recruitment is not linked to the number of biopsies collected and may continue up to a maximum of 37 subjects even if 15 fresh tumor biopsies have already been obtained. The benefit/risk balance will be evaluated on an ongoing basis in this cohort.

More details can be found in section 10.9 Sample Size Estimation of the protocol final version 10.0, dd. 9 December 2019.

4. General Analysis Definitions

Data will be analyzed using SAS (Version 9.4 or higher). For graphs R (Version 3.3.2 or higher) can be used in addition.

Descriptive statistics will be tabulated as follows:

- Categorical data will be summarized in contingency tables presenting frequencies and percentages.
- Continuous data will be summarized using number of non-missing values (n), mean, standard deviation, median, 25th and 75th percentiles, minimum and maximum values.
- Time to event parameters will be described using Kaplan-Meier estimates: median time, first and third quartiles along with approximate 95% confidence intervals (the default conftype=loglog in proc lifetest will be used). The 3, 6, 9 and 12 months event-free rates will also be presented together with the 95% confidence intervals.

Page 8 of 46

TPL N°: eTPL SA-02-01 Of SOP SA-02.08 TPL Effective Date: 31 Mar 2016 TPL Version: 02

The results will be presented by 1Q3W and 3Q4W dose-escalation and expansion parts separately. Results will be presented for both trial parts unless specified otherwise.

The results will be presented by groups and total. In the dose-escalation 1Q3W and 3Q4W arms of the trial, groups are defined by dose levels. In the expansion part, groups are defined by cohort, dose level and dosing regimen.

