4.6 Calculated Variables

The following general definitions will be used throughout the trial:

 Baseline is defined as the latest recorded measurement made before the first IMP administration (trial day 1). Measurements done on the same date as the first IMP administration will be considered as done before the first IMP administration unless specified otherwise. For PK variables, the first IMP administration will be time 0.

TPL N°: eTPL SA-02-01 TPL Version: 02

Of SOP SA-02.08
TPL Effective Date: 31 Mar 2016
Approved in Vault: 6/30/2021

- Change from baseline is defined as the post-baseline value baseline value. Change from baseline will be missing when either post-baseline or baseline value is missing.
- Percent change from baseline is defined as 100*(post-baseline value baseline value)/baseline value. If the baseline value is 0 and the post-baseline value is 0, the change from baseline and the percent change from baseline are both 0. If the baseline value is 0 and the post-baseline value is not 0, the change from baseline is the same as the post-baseline value and the percent change from baseline will be undefined (missing).

The following variables will also be computed for the analyses described later on:

- Time (in months) from initial diagnosis of primary site to start date of IMP: (date of first IMP administration date of first diagnosis)/30.4375.
- Time (in months) since most recent recurrence/relapse or progression to start date of IMP: (date of first IMP administration – date of most recent recurrence/relapse or progression)/30.4375.
- Time (in months) since (last) biopsy to start date of IMP: (date of first IMP administration date of (most recent) biopsy before or on the start date of IMP)/30.4375. Time since biopsy will be included in the listing, time since last biopsy will be included in the biopsy table (only one result per subject).
- Time (in months) since biopsy to start date of IMP for post-baseline biopsy data: (date of (most recent) biopsy date of first IMP administration +1)/30.4375.
- Time (in months) since most recent recurrence/relapse or progression to date of most recent biopsy: (date of most recent biopsy date of most recent recurrence/relapse or progression)/30.4375.
- Time (in months) between fresh biopsy and archival biopsy (when both are available): (date of fresh biopsy date of archival biopsy)/30.4375 (only listed).
- Duration of exposure (days): (end date of IMP date of first IMP administration + 1),

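### The percent-change summary of Axl H-score keeps zero-baseline tumours that stay at zero and drops those that rise, so it omits every increase from an Axl-negative baseline

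*SAP*

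**What the plan says.** SAP section 15.7 (Tumor Axl-Expression – Expansion Part) states: "Descriptive statistics (actual values and percent change from baseline) will be presented to summarize the H-score parameters". The scores are for membrane and cytoplasm, at baseline and over time. The graphical summary matches: "Mean-se plots over time will be done for the actual values and percent change from baseline". No absolute change from baseline appears in the visible text of that section, and neither does a count of patients left out of the percent change.

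The derivation is in SAP section 4.6 (Calculated Variables), introduced by "The following general definitions will be used throughout the trial". Two of its rules concern a zero baseline:

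- Zero followed by zero: "If the baseline value is 0 and the post-baseline value is 0, the change from baseline and the percent change from baseline are both 0".
- Zero followed by a non-zero value: the absolute change equals the post-baseline value, but "the percent change from baseline will be undefined (missing".

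Section 15.7 makes no exception for H-score. For CA-125, by contrast, SAP section 15.5 plans: "Descriptive statistics (actual values, change from baseline and percent change from baseline) will be presented".

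**The concern.** A staining score such as the H-score has a floor at zero. A tumour that starts at zero can therefore do only two things: stay at zero or rise. The rule keeps the first group as 0% and removes the second. Whether a zero-baseline patient counts is thus decided by the outcome, and every patient removed this way is one whose expression increased.

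Percent change is the only within-patient measure in the visible text of section 15.7, so no paired summary there shows an Axl-negative tumour becoming positive. Axl expression in the biopsy is a secondary endpoint (Protocol section 4.5), and markers of response and resistance are the exploratory objective (Protocol section 4.3). A switch from negative to positive under treatment is relevant to both.

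**Working it through.** The plan states no figure on this point, so there is nothing to reproduce. The rule was applied directly. **All H-score values below are hypothetical.**

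**Rule.** With baseline b and post-baseline p:
- b > 0: percent change = 100 × (p − b) / b
- b = 0 and p = 0: 0%
- b = 0 and p > 0: missing
- absolute change = p − b in every case

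**Example A: 10 pairs** (four 0→60, two 0→0, four 100→50).
- Mean absolute change: (4×60 + 2×0 − 4×50) / 10 = +4 points.
- SAP rule: (0 + 0 − 4×50) / 6 = −33.3%, n = 6.
- Actual values by visit: baseline 400/10 = 40; post-baseline (240 + 0 + 200)/10 = 44.
- All zero baselines set to missing: −50%, n = 4.

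**Example B: 20 pairs** (12 with baseline 100, 8 with baseline 0).

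| Baseline-100 tumours | Zero baselines rising to 60 | SAP rule | Mean absolute change |
|---|---|---|---|
| unchanged | 4 of 8 | 0.0% (n = 16) | 240/20 = +12 |
| fall 30% | 4 of 8 | −360/16 = −22.5% (n = 16) | (240 − 360)/20 = −6 |
| fall 30% | 8 of 8 | −30% (n = 12) | (480 − 360)/20 = +6 |

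In the last row the two measures have opposite signs.

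**Range over the unknown share of zero baselines.** Let q be the share, with half of those tumours rising to 60 and positive baselines unchanged. Mean absolute change = q × 0.5 × 60 = 30q.

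| q | Mean absolute change | SAP rule |
|---|---|---|
| 5% | +1.5 | 0.0% |
| 10% | +3 | 0.0% |
| 20% | +6 | 0.0% |
| 40% | +12 | 0.0% |

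**Simulation with no true change.** Assumptions: latent mean 30, 60 or 100; between-tumour SD 60; measurement SD 30; scores rounded and limited to 0–300; 400,000 pairs each.

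| Latent mean | Pairs dropped | Absolute change, all pairs | Retained pairs | Dropped pairs | Mean percent change, SAP rule |
|---|---|---|---|---|---|
| 30 | 9.3% | −0.01 | −2.9 | +28.7 | +33.8% |
| 60 | 6.8% | −0.03 | −2.3 | +31.1 | +34.0% |
| 100 | 3.3% | +0.01 | −1.2 | +34.2 | +25.9% |

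The retained pairs show a spurious fall in points, which is the selection effect. The mean percent change is nevertheless positive, because small positive baselines produce very large values: 1→150 is 100 × 149/1 = +14,900%. The median percent change was 0.0 in all three settings. The two distortions pull in opposite directions.

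**The case against.** The strongest reply is that nothing is lost from the report as a whole. Section 15.7 plans actual values by time point, mean-SE plots of them and a listing. SAP section 4 adds: "Continuous data will be summarized using number of non-missing values (n), mean, standard deviation, median". A smaller n for percent change would therefore signal that patients had dropped out. In Example A the actual-value rows would show 40 rising to 44. This stands: a reader might infer that the increases disappear altogether, and the documents do not support that. What it leaves open is that means by visit are not paired once later biopsies are missing, and a smaller n does not say that every patient dropped for a zero baseline was a riser.

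A reader might also infer that the reported mean is biased downward. That holds only for the selection effect, measured against all paired patients. The simulation means of +26% to +34% with no true change show that the net direction is not fixed. Compared with excluding every zero baseline, the retained 0% values can even move the mean upward (−22.5% against −30% in Example B).

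Zero baselines may be uncommon. Protocol section 3.1 bases the choice of indications on Axl expression, and Protocol Appendix I reports expression in most tissues from melanoma that had relapsed on, or was refractory to, BRAF inhibitors. Its report of little or no expression concerns predominantly early-stage melanoma. On the other side, the expansion eligibility criteria (Protocol section 6.1) set no expression threshold, Protocol section 8.5.10 describes Axl as dynamic and heterogeneous, and membrane and cytoplasm are scored separately. Neither side yields a number.

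Finally, the endpoint is worded as expression, not change in expression. No test, sample size or decision rule depends on this summary. SAP sections 15.8 and 18 and several Axl-related outputs are blacked out and may contain other analyses, so the absence of absolute change can be stated only for the visible text.

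**Conclusion.** The point holds in a limited form. The percent-change tables and plots for H-score select patients by outcome and omit every increase from an Axl-negative baseline. This follows from sections 4.6 and 15.7 read together, given that an H-score cannot be negative, and needs no assumption about the data.

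The size does need one. It is nil if no tumour has a zero baseline. Under the assumptions in the range table, it is a mean rise of 1.5 to 12 points reported as 0.0%. A sign conflict is possible but requires particular hypothetical mixes, so it illustrates the rule and does not predict the result. The documents support neither a general claim of downward bias nor a claim that the increases are absent from the report. The consequence is confined to a descriptive secondary endpoint. The change is still worth making, because the paired summary leaves out a group of direct interest and the remedy is already defined in the SAP.

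**What to change.** - In SAP section 15.7, add paired absolute change from baseline in H-score points to Tables 14.02.10.a and 14.02.10.b and to the mean-SE plots, as the main change summary. Section 4.6 already defines it for zero baselines, and section 15.5 already plans it for CA-125.
- Report, by visit, how many patients move from 0 to above 0, move from above 0 to 0, or stay at 0.
- If percent change is also kept, set it to missing for every zero-baseline patient and state how many are excluded. Do not present it alone. Uniform exclusion removes the dependence on outcome but does not recover the increases; in Example A it moves the mean from −33.3% to −50%, against an absolute change of +4 points.

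The cost is a sentence or two in the SAP, one derivation that is already specified, and some added table rows and plots. No new data are needed. The SAP addendum (section 2.1) says data up to the March 2021 cut-off have already been reported, so in practice this would be a supplementary output from existing data.
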